## 3.4.3 Choice of Study Eye in Cases of Bilateral Eligibility

If both eyes of a participant meet the eligibility criteria, the investigator will choose to enroll one eye in consultation with the participant.

#### 3.5 Outcome Measures

#### 3.5.1 Primary Study Outcome

The primary outcome for the study is the safety of the combination investigational treatment, assessed by tabulation of adverse events (AEs) reported through Week 52.

#### 3.5.2 Secondary Study Outcomes

Secondary outcomes include tabulation of AEs reported through Week 104 and the following measures in the study eye at Weeks 52 and 104:

- the proportion of participants experiencing reduction in size of at least one RCH in the absence of other ablative treatment (assessed by fundus photography and FA);
- the proportion of participants experiencing moderate vision loss (defined as a loss of ≥ 15 letters from baseline on electronic visual acuity [EVA] testing);
- mean change in visual acuity;
- change in size of RCH (measured by fundus photography and FA);

- change in exudation (measured by fundus photography, Optical Coherence Tomography [OCT] and FA);
- change in epiretinal proliferation, fibrosis or retinal traction (assessed by OCT and fundus photography);
- the proportion of participants undergoing ablative treatment of RCH or ocular surgery;
- the proportion of participants with successful ablative treatment of RCH; and
- the proportion of participants with appearance of one or more new RCH.

## 4.0 STATISTICAL CONSIDERATIONS

Since this is a proof-of-principle study, all analyses will be exploratory in nature.

## 4.1 Sample Size

The accrual goal is three participants. This is an appropriate sample size for the study objectives, since this preliminary investigation will not attempt to definitively determine the safety or efficacy of this treatment.

#### 4.2 Analysis Population

All enrolled participants who received at least one study treatment injection, regardless of whether they discontinued treatment prior to Week 52, will be included in the analysis population. All summaries and listings will be based on the primary analysis population.

#### 4.3 Descriptive Statistics

For continuous parameters, descriptive statistics will include number of observations, mean, standard deviation, median, minimum and maximum. For categorical parameters, frequency and percentage of participants will be summarized; percentages will be based on the number of participants in the primary analysis population.

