4.3 Study Design

This study will examine the effect of multiple E10030 and ranibizumab injections in participants with severe ocular VHL disease. A single study eye in each participant will receive combination treatment consisting of intravitreal injections of E10030 (1.5 mg in 0.05 mL) and ranibizumab (0.5 mg in 0.05 mL) (given as separate injections during the same procedure, meaning that participants will receive two intravitreal injections per visit, see Appendix 3) every four weeks from baseline through Week 16 (totaling five treatments) and then every eight weeks through Week 48 (totaling nine treatments from baseline). The primary endpoint will be assessed by tabulation of AEs reported through Week 52. During the second year, all participants will be seen at Weeks 60, 72, 84 and 104. Starting after Week 52, participants may return for additional visits

in the second year of the trial, as often as every four weeks, for evaluation and for administration of standard of care therapies, at investigator discretion. No further administration of investigational product will occur after the Week 48 visit. Participants will have a minimum of 14 study visits at the NEI outpatient clinic. The baseline study visit will require approximately five hours, and the subsequent visits will require approximately three to four hours each.

Standard of care therapies will be considered for significant clinical worsening at any time during the study, for clinical improvement starting at Week 16 (as in a case where clinical improvement makes an eye more amenable to ablative or surgical treatment), and without restriction starting at Week 40 (in anticipation of unavailability of investigational product after Week 48). Any participants who discontinue combination investigational treatment will be asked to return for all study visits and will be included in the analyses at the end of the study.

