7.2 Individual Withdrawal Criteria

Participants may choose to withdraw from this study for any reason at any time without penalty, loss of benefits or prohibition from enrolling in other clinical protocols. Reasons for participant discontinuation of combination investigational product or withdrawal may include, but are not limited to, the following:

- Visual acuity loss of \geq 30 letters from baseline;
- Investigator determination that it is not in the best medical interest of the participant to continue participation;
- Findings in the course of the trial that may affect willingness to participate;

- Inability to keep study visits or to comply with study requirements;
- Participant requires ocular surgery which cannot safely be postponed until the end of the study;
- Pregnancy;
- An adverse reaction to the study treatment or a serious complication associated with or aggravated by continuation of one or both investigational products;
- Cardiovascular event or stroke; or
- Other safety concerns.

Discontinuation of the combination investigational treatment does not necessitate study withdrawal. Whenever possible, investigators will ask study participants discontinuing combination investigational treatment to continue to return for study visits.

7.3 **Pregnancy Monitoring**

If an investigator becomes aware that a female study participant has become pregnant during the study, no further intravitreal injections of combination investigational treatment will be administered. The investigator and participant will determine whether to continue any remaining study visits or to exit the study.

If an investigator becomes aware that a male study participant has impregnated his partner during the study, the investigator will remind the participant of the potential risks to the unborn fetus.

In either case of reported pregnancy, participant (or partner) will be referred to the NIH OB/GYN consultation service for evaluation and counseling. The investigator must follow the participant (or partner) until the pregnancy outcome.

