## 3.0 GENERAL REVIEW OF STUDY DESIGN

## 3.1 Study Design

The ER-VHL study is a phase I/II, single-center, prospective, open label, non-randomized, uncontrolled, single group trial investigating the safety and potential efficacy of combined treatment of severe ocular VHL disease with serial intravitreal injections of E10030 and ranibizumab.

The study will require a minimum of 14 visits (baseline and Weeks 4, 8, 12, 16, 24, 32, 40, 48, 52, 60, 72, 84 and 104). All visits must be conducted within a window of  $\pm$  seven days from the target day through Week 52 and  $\pm$  30 days thereafter. Prior to treatment at each visit, the participant will undergo an AE assessment, concomitant medication review, vital sign check and ophthalmic evaluation.

A single study eye in each participant will receive combination treatment consisting of intravitreal injections of E10030 (1.5 mg in 0.05 mL) and ranibizumab (0.5 mg in 0.05 mL) (given as separate injections during the same procedure, meaning that participants will receive two intravitreal injections per visit) every four weeks from baseline through Week 16 (totaling five treatments) and then every eight weeks through Week 48 (totaling nine treatments from baseline). The primary endpoint will be assessed by tabulation of AEs reported through Week 52. Starting after Week 52, participants may return for additional visits in the second year of the trial, as often as every 4 weeks, for evaluation and for administration of standard of care therapies, at investigator discretion; all participants will be seen at Weeks 60, 72, 84 and 104. No further administration of investigational product will occur after the Week 48 visit.

Participants will be monitored at each visit for injection-related complications such as endophthalmitis, retinal tear/detachment, intraocular hemorrhage, cataract and glaucoma and for any progression of ocular VHL disease; participants who develop such complications may be discontinued from receiving the combination treatment. They will also be monitored at each visit for intraocular inflammation (as assessed by presence of anterior chamber or vitreous cell on ophthalmoscopy).

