Concomitant therapies for non-ocular conditions are allowed without restriction. If systemic treatment with either anti-VEGF or anti-PDGF therapy is required, interruption or discontinuation of combination investigational treatment will be considered and discussed with other treating physicians. Any participant who discontinue study treatment will be asked to return for all future study visits.

Standard care therapies for VHL disease, including laser photocoagulation, cryotherapy, photodynamic therapy, surgery, ocular radiation and any medication use associated with these treatments (such as use of systemic corticosteroids to minimize exudation from RCH undergoing ablative treatment) will be considered for significant clinical worsening at any time during the study, for clinical improvement at any time starting at Week 16 (as in a case where clinical improvement makes an eye more amenable to ablative or surgical treatment), and without restriction starting at Week 40 (in anticipation of unavailability of investigational product after Week 48).

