#### 9.2 **Post-Injection Evaluation**

Intraocular pressure (IOP) in the injected eye is measured by Tono-Pen within 20 minutes after injection. Post-injection IOP and change from pre-injection measurement will be summarized for each visit (Table 10). Frequency and percentage of participants with the following will be presented for each visit:

- > 24 mmHg IOP after injection in the treated eye (Table 10);
- Severe pain, absence of hand-motion vision or absence of perfusion of the retinal arterioles following an injection (Table 9);
- Intraocular inflammation as assessed by the presence of anterior chamber or vitreous cell on ophthalmoscopy by grade (Table 9); and
- Any other complications following an injection (Table 9).

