# Table 10: Summary of IOP Over Time

					Post-Injection IOP		
	Pre	Pre-Injection IOP Measurements				Measurements	
	(mmHg)				(mmHg)		
		Change from					
	Baseline in Pre- Injection						
	Pre-Injection IOP		Measurements		Study Eye		
					Post-	Change from	
	Study	Non-Study	Study	Non-Study	Injection	Pre-Injection	
	Eye	Eye	Eye	Eye	IOP	Measurement	
Week 104							
N	Х	Х	Х	Х			
Mean (SD)	x.x (x.x)	x.x (x.x)	x.x (x.x)	x.x (x.x)			
Median	X.X	X.X	X.X	X.X			
Range (Min, Max)	x.x, x.x	x.x, x.x	x.x, x.x	X.X, X.X			
 Denominators are the number of participants in the primary analysis population.							

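### Per-visit post-injection percentages (SAP 9.2, Tables 9 and 10) are divided by all treated participants, including any not injected at that visit

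*SAP*

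**What the plan says.** SAP 4.2 defines the analysis population as enrolled participants with at least one study injection, whether or not they later stopped. SAP 4.3 then sets a general rule for categorical results: "percentages will be based on the number of participants in the primary analysis population". The Table 10 footnote restates it, "Denominators are the number of participants in the primary analysis population", and Table 9 carries the same footnote.

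SAP 9.2 uses this rule visit by visit: "Frequency and percentage of participants with the following will be presented for each visit". The list covers post-injection intraocular pressure (IOP) above 24 mmHg (Table 10). It also covers three Table 9 items: severe pain, absent hand-motion vision or absent retinal perfusion; intraocular inflammation by grade; and any other post-injection complication.

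The documents also provide for participants who attend without being injected:

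- Under SAP 3.1, if systemic anti-VEGF or anti-PDGF therapy is required, "interruption or discontinuation of combination investigational treatment will be considered and discussed with other treating physicians".
- SAP 3.1 says of injection-related complications and disease progression that "participants who develop such complications may be discontinued from receiving the combination treatment".
- Protocol 7.2 states: "Discontinuation of the combination investigational treatment does not necessitate study withdrawal".
- Protocol 4.3 states: "Any participants who discontinue combination investigational treatment will be asked to return for all study visits". SAP 3.1 has an equivalent sentence.

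**The concern.** A post-injection event can happen only to someone who was injected at that visit. A participant who attends a scheduled injection visit without injection cannot contribute to the numerator, but the rule keeps that person in the denominator as event-free. The percentage then no longer describes the risk of the procedure at that visit, and for a safety rate the error can only be downward.

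The shells already recognise the principle for visits. At Week 104, when no injection is scheduled, the post-injection cells of Tables 9 and 10 are blank. The same logic is not carried through to a participant who is not injected at a visit where others are.

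These are the plan's direct per-visit summaries of giving two intravitreal injections in one procedure. At stake is whether a reader can take the percentage at face value.

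**Working it through.** **Inputs**

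- N, participants treated: 3, if the accrual goal in SAP 4.1 is met and all three receive at least one injection.
- Scheduled injection visits (SAP 3.1; Protocol Appendix 2): Weeks 0, 4, 8, 12 and 16 (five), then 24, 32, 40 and 48 (four). 5 + 4 = 9, which matches the nine treatments the plan states. The problem can arise only at these visits.
- n, participants injected at a given visit: an assumption. The documents give no discontinuation or interruption rate.
- e, participants with the post-injection event at that visit.

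The plan states no percentage to reproduce, so the check compares two denominators.

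**Formulas**

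- Printed rate (SAP 4.3 and footnotes) = e / N
- At-risk rate = e / n
- Therefore printed rate = at-risk rate × (n / N)

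**Results for N = 3**

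| Injected n | Events e | Printed e/3 | At risk e/n |
|---|---|---|---|
| 3 | 1 | 1/3 = 33% | 1/3 = 33% |
| 3 | 2 | 2/3 = 67% | 2/3 = 67% |
| 2 | 0 | 0/3 = 0% | 0/2 = 0% |
| 2 | 1 | 1/3 = 33% | 1/2 = 50% |
| 2 | 2 | 2/3 = 67% | 2/2 = 100% |

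With two injected, the factor n/N is 2/3, so the printed rate cannot exceed 67% even if every injected eye has the event. With all three injected, or with no event, the two rates agree.

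**What a reader can recover**

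- Table 10 prints N for post-injection IOP in the same column and visit block as the percentage above 24 mmHg. Protocol Appendix 3 has IOP measured within 20 minutes of injection, so that N is the number injected unless a reading was missed.
- The Table 9 cell grades include a category for grade 0 or trace, so counts across grades sum to the number examined in that eye. That is not the number injected.
- The two Table 9 post-injection columns print no N.

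**Which denominator suits which row**

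Anterior chamber and vitreous cells appear in the same SAP 9.2 list but do not require an injection. They are tabulated for both eyes and through Week 104, so their per-visit denominator should be participants examined. The Table 9 row for events occurring at least once in the study is cumulative, and all treated participants is the right base there.

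**The case against.** The strongest reply is that this hardly matters. The trial has three participants, SAP 4.0 calls all analyses exploratory, and SAP 7.0 and 8.0 plan no formal analysis. No decision rule uses these percentages. Every cell shows a count beside the percentage, and the denominator is footnoted, so one of three is a correctly labelled share of those treated. Injections are listed by visit (SAP 6.0), discontinuations are listed with timing and reason (SAP 9.7), and raw data are listed by participant (SAP 12.5). The adverse event tables already separate time on treatment from time after discontinuation (SAP 7.0, Table 3). All of this stands, and it limits the importance of the point. It does not make the per-visit percentage a rate among those at risk.

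It could also be said that SAP 4.4 deals with the matter by excluding missing observations. It does so only in general terms and does not override the explicit rule in SAP 4.3 or the footnotes.

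A reader might infer that, because complications can lead to stopping, the rule hides an informative loss that a new denominator would repair. The first half is possible under SAP 3.1. The second is not: dividing by those injected leaves later visits with the participants who tolerated injection, and that selection remains. The change corrects the arithmetic of the rate and nothing more.

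**Conclusion.** The point holds, and it is small. The stated rule multiplies the at-risk per-visit post-injection rate by n injected over N treated. With one of three not injected, 33% stands in for 50%, or 67% for 100%. This assumes three treated participants, at least one uninjected at a scheduled injection visit, and an event at that same visit. Otherwise there is no effect. The main practical gap is the Table 9 post-injection columns, where no N is shown.

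Three stronger readings are tempting, and the documents do not support them:

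- A reader might infer a contrast of 33% against 100%. It is arithmetically possible with one injected, but it needs two of the three uninjected at the same visit, and nothing in the documents makes that an expected case.
- A reader might infer that the safety results as a whole are understated. The adverse event tables, including the primary outcome, are cumulative, and all treated participants is their proper base.
- A reader might extend the complaint to the Week 52 and Week 104 outcomes. Table 7 has a separate cell for each participant, so an absent assessment can be seen there, and Table 8 prints N for visual acuity. At most, Table 7 could also print the number assessed.

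**What to change.** Amend SAP 4.3 and the footnotes to Tables 9 and 10 as follows.

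- For per-visit post-injection rates (IOP above 24 mmHg in Table 10; the two post-injection columns of Table 9), divide by participants injected and evaluated at that visit, and print n/N.
- For anterior chamber and vitreous cells in Table 9, divide by participants examined at that visit, and print n/N.
- Keep all treated participants as the denominator for cumulative summaries: adverse event Tables 3 to 6, the at-least-once row of Table 9, and ablative treatment or ocular surgery in Table 7.
- Optionally, print the number assessed in Table 7.

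The cost is SAP wording, footnotes and a printed n/N. No new data are needed and trial conduct does not change. The downside is that some percentages will rest on one or two participants, which the printed n/N makes visible.

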## 4.4 Handling of Missing Values

In general, missing observations will be excluded from analyses.

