#### 8.3 Electronic Visual Acuity (EVA)

Binocular visual acuity measures and visual acuity measures for each eye will be obtained using an EVA algorithm. EVA with manifest refraction will be performed if a change in EVA  $\geq$  10 E-ETDRS letters ( $\geq$  0.20 logMAR) since previous visit is observed.

Summary statistics for change in total letters read at Weeks 52 and 104 compared to baseline will be presented. Frequency and percentage of participants with moderate vision loss at Weeks 52 and 104, defined as loss of  $\geq$  15 letters from baseline, will also be summarized (Table 8). Values from assessments performed with manifest refraction will be used for the analysis if available; otherwise, values from assessments performed without manifest refraction will be used.

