# Table 7: Analysis of Secondary Outcomes Relating to RCH (Continued)

		Change from Baseline						
	Baseline	Week 52	Week 104					
EVA Total Letters Read								
N	Х	Х	Х					
Mean (SD)	x.x (x.x)	x.x (x.x)	x.x (x.x)					
Median	Х	Х	Х					
Range (Min, Max)	X, X	х, х	х, х					
Participants with Moderate Vision Loss		x (x%)	$\mathbf{x} (\mathbf{x}^{0/2})$					
(Loss of $\geq$ 15 Letters Read from Baseline),								
$\frac{N}{2}$								

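### A treated participant with no Week 52 or Week 104 acuity counts as 'no loss' in the Table 8 vision-loss percentage, because SAP 4.3 fixes the denominator while SAP 4.4 drops missing values

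*SAP*

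**What the plan says.** Four parts of the SAP act on this percentage.

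- **Who is analysed.** SAP 4.2 takes everyone who had at least one injection; they, "regardless of whether they discontinued treatment prior to Week 52, will be included in the analysis population".
- **Denominator.** SAP 4.3, on categorical summaries: "percentages will be based on the number of participants in the primary analysis population".
- **Missing values.** SAP 4.4, in full: "In general, missing observations will be excluded from analyses". It gives no imputation rule and does not mention denominators.
- **The outcome.** SAP 8.3 calls for "Frequency and percentage of participants with moderate vision loss at Weeks 52 and 104", meaning a loss of 15 letters or more from baseline. Its only rule for choosing a value is to prefer acuity taken with manifest refraction. It does not say what to do when there is no acuity at all.

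The Table 8 shell (SAP 12.3) has a row labelled "Participants with Moderate Vision Loss" with a count and percentage at each of the two weeks. Above it, in the same columns, are the letter-change statistics with their own N. There is no row for participants not assessed.

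Other shells apply the fixed denominator openly. The Table 10 footnote reads "Denominators are the number of participants in the primary analysis population", and it covers counts at single visits. Tables 7 and 9 carry equivalent footnotes. The Table 7 outcomes with a two-way answer allow only Yes or No.

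**The concern.** A percentage at a visit normally describes the participants seen at that visit, or else it states how the others were handled. Here two general rules, each reasonable alone, combine into a handling that nobody has stated: absence of a measurement acts as absence of the event. Because the event is vision loss, the effect is favourable to the treatment whenever a loss is seen in another eye.

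Missing acuity is foreseeable. Protocol 4.5.1 expects occasional missed assessments and visits. Protocol 7.2 lists a loss of 30 letters or more among possible reasons for stopping product or withdrawing, so absence may be related to vision. With three participants, each absence is a third of the denominator.

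One column of Table 8 could also rest on two bases without saying so: letter change on the two assessed, and the loss percentage just below on all three treated.

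**Working it through.** **Plan's own figure.** There is none to reproduce. The documents state no expected loss rate, dropout rate or power.

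**Inputs**
- N = 3 treated: accrual goal in SAP 4.1, assuming all three receive an injection (SAP 4.2).
- Denominator = N: SAP 4.3.
- Missing acuity cannot be counted as a loss: SAP 4.4.
- m = number without acuity at the visit, L = number seen to have lost 15 letters or more. The documents give no values for these, so the patterns below are assumed for illustration.

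**Formulas**
- Printed under SAP 4.3 and 4.4: L / N.
- Printed if each missing participant were recoded as no loss: (L + 0·m) / N = L / N. This is identical to the first formula for every L and m.
- Among those assessed: L / (N − m).
- Range consistent with the data when the missing eyes are unknown: L / N to (L + m) / N.

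**Results, N = 3**

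| Missing m | Losses seen L | Printed L/3 | Missing recoded as no loss | Among assessed | Possible range |
|---|---|---|---|---|---|
| 1 | 0 | 0/3 = 0% | 0% | 0/2 = 0% | 0% to 33.3% |
| 1 | 1 | 1/3 = 33.3% | 33.3% | 1/2 = 50.0% | 33.3% to 66.7% |
| 1 | 2 | 2/3 = 66.7% | 66.7% | 2/2 = 100% | 66.7% to 100% |
| 2 | 0 | 0/3 = 0% | 0% | 0/1 = 0% | 0% to 66.7% |
| 2 | 1 | 1/3 = 33.3% | 33.3% | 1/1 = 100% | 33.3% to 100% |

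**What the table shows**
1. The printed value equals the recoded value in every row. It is always the lower end of the possible range.
2. The denominator changes the percentage only when at least one loss is seen. With one missing and one loss the difference is 50.0 − 33.3 = 16.7 percentage points.
3. With no loss seen, the percentage is 0% on either base. What is wrong is the 3 in 0/3, since only two eyes were examined.
4. A study exit before Week 52 affects both Table 8 cells. An exit after Week 52, or one missed visit, affects one.

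**Reach beyond Table 8.** Table 11 has a row for loss of 15 letters or more at each visit from Week 4, and SAP 4.3 gives it the same base. The Table 7 footnote does so explicitly. In its Yes/No rows a participant who was not assessed has no valid entry, and if left blank is still in the denominator.

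**The case against.** **The rules can be read differently.** Nothing in the SAP says outright that missing acuity means no loss. SAP 4.4 speaks only in general terms, and exclusion could mean removal from the denominator too. Any footnote under Table 8 cannot be read in the available copy. This stands as a caution about wording. But SAP 4.3 sets the denominator explicitly for all categorical summaries, and Tables 9 and 10 use it for counts at single visits. If the sponsor intends the other reading, the SAP still needs a sentence saying so.

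**The gap is visible.** Table 8 prints N for letter change directly above the loss row. SAP 9.7 lists withdrawals with timing and reason, and SAP 12.5 lists raw data by participant. This stands, and it is the main reason the point is minor.

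**The trigger is narrow.** Protocol 4.3 says that those who stop product "will be asked to return for all study visits and will be included in the analyses at the end of the study". Only full exits and missed Week 52 or 104 assessments matter, and the documents give no probability for either. This stands.

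**A stronger reading is tempting.** A reader might infer that if someone leaves after losing 15 letters or more, Table 8 understates the result by a full third: 0/3 against 1/3, or 1/3 against 2/3 if another eye also has a loss. The reader might then ask for a row based on last acuity before exit. The documents do not support this. The outcome is status at Weeks 52 and 104, and a leaver's status then is unknown; an earlier loss may have been transient. The one-third gap also mixes the denominator effect with a change of endpoint: in the first case the denominator contributes nothing, since 0/3 and 0/2 are both 0%. Acuity is scheduled at every visit, so a loss recorded at a scheduled visit before exit is already counted in Table 11 at that visit, and it appears in the listings.

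**Conclusion.** The point holds and is minor. Under SAP 4.2 to 4.4 as written, a treated participant without Week 52 or Week 104 acuity is counted exactly as one with no loss. With three treated, one missing and one loss, the plan prints 33% where 50% of those assessed had a loss. With no loss seen, the percentage is unchanged and only the implied number assessed is wrong.

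This rests on three assumptions: that all three participants are treated, that at least one lacks acuity at Week 52 or 104, and that the explicit denominator rule in SAP 4.3 governs Table 8. The percentage among those assessed is not an estimate of what a missing eye would have shown; it simply describes the eyes that were examined.

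A reader should not conclude that the SAP deliberately imputes success, or that the result is biased by a known amount. SAP 4.0 and 8.0 call the analyses exploratory, with no formal testing of these outcomes. No decision depends on this percentage, and the primary adverse-event outcome through Week 52 is unaffected.

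**What to change.** - **SAP 4.3/4.4:** add that, for outcomes assessed at a visit, the percentage uses the number assessed at that visit, with the number not assessed shown beside it. Adverse-event tables keep all treated participants as the base.
- **Tables 8 and 11:** print the loss row as count over number assessed, followed by the number not assessed, for example 1/2 (50%), 1 not assessed.
- **Table 7:** allow *not assessed* as an entry beside Yes and No, and change the footnote to match.

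No last-acuity row is needed, because Table 11 and the listings already show losses recorded before exit.

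The cost is one or two sentences and small changes to three table shells, with no new visits, data or participants. The drawback is that denominators will differ between visits and outcomes, so each must be printed.
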